2.0 SCHEMA

This study will have 2 strata: Stratum 1 is for patients with osteosarcoma. Stratum 2 is for patients with other high risk solid tumors metastatic to bone.

3.0 OBJECTIVES

3.1 PRIMARY OBJECTIVES

3.1.1 (Stratum 1 Only)

To assess the clinical response of high-risk osteogenic sarcoma to high-dose ^{153}Sm -EDTMP and external beam adiotherapy.

3.1.2 (Stratum 2 Only)

To estimate the response rate of diseases other than osteosarcoma to the combination of high-dose ^{153}Sm -EDTMP and external beam radiotherapy.

3.2 SECONDARY OBJECTIVES

3.2.1 To describe the toxicity and long-term effects of combined infusional ^{153}Sm -EDTMP and external beam radiation therapy.

3.2.2 To image tumors using [^{18}F]Fluoromisonidazole (^{18}F -MISO) PET scanning before and after treatment, and compare with clinical response as measured by radiographic imaging and/or histology.

3.2.3 To describe the distribution of absorbed doses delivered to each targeted lesion and the distribution of lesion equivalent uniform dose delivered to each patient.

3.2.4 To determine dosimetry measurements after initial tracer dosing, predict target total radiation exposure to tumor based on linear kinetics previously described, and calculate a subsequent combined treatment dose.

3.2.5 Stratum 1 Only

To observe overall survival and time to progression in patients treated with combined infusional ^{153}Sm -EDTMP and external beam radiation therapy, and model any relationship between total absorbed dose and progression.

4.0 INTRODUCTION

4.1 GENERAL BACKGROUND

Cure of osteogenic sarcoma relies on both definitive control of gross tumor masses and on effective treatment of micrometastatic disease. While systemic chemotherapy can be effective in the control of micrometastases, surgery is usually required to treat gross disease. Osteogenic sarcoma is relatively resistant to radiation therapy, limiting the utility of this treatment modality for local control. A mechanism to deliver radiation therapy at a high enough dose to be tumoricidal while sparing surrounding normal tissue would allow the incorporation of radiation

into the therapeutic armamentarium when up-front surgery is not feasible. In the event of good tumor shrinkage, this might allow for subsequent surgical intervention or other localized therapy such as cryoablation.

Studies of radiation therapy in osteogenic sarcoma were performed prior to 1980, and demonstrated that doses in the range of 66-80 Gy are required for a therapeutic response. Several studies point out that administration of less than 60 Gy is associated with only transient tumor control, and viable tumor has been found in amputation specimens even after treatment with 80 Gy or more (1-3). These doses are quite difficult to deliver using standard external beam radiation without exceeding the tolerance of surrounding normal tissue. Because of this, standard treatment regimens for osteogenic sarcoma do not incorporate radiation therapy. Even modern conformal techniques, such as intensity-modulated radiation therapy (IMRT) are of limited utility in the setting of multiple metastases, and are unable to treat micrometastatic disease. This is a hindrance to the cure of patients with multiple sites of metastatic disease or with unresectable tumors for which surgery will not provide complete control of gross disease.

Targeted radioisotope delivery has been pursued as an alternative to external beam radiotherapy for osteogenic sarcoma or to supplement external beam radiotherapy. One of the most promising agents being developed for this purpose is ^{153}Sm ethylenediaminetetramethylene phosphonic acid (^{153}Sm -EDTMP). This compound localizes to sites of new bone formation similar to technetium-99m methylene diphosphonate ($^{99\text{m}}\text{Tc}$ -MDP) bone scintigraphy. The EDTMP moiety is structurally related to the chelating agent methylene diphosphonate that is complexed to technetium-99 for conventional bone imaging. This allows the delivery of radiotherapy to osseous metastatic lesions visible on conventional bone scan (4). A medium energy photon given off by the ^{153}Sm -EDTMP allows for standard scintigraphic scanning to monitor the delivery of radiation to the tumor.

Other characteristics of ^{153}Sm that make it of interest in the treatment of osteogenic sarcoma are the emission of tumoricidal beta radiation and a relatively short half-life. The tumoricidal beta radiation of ^{153}Sm is emitted at maximum energies of 640, 710, and 810 keV (32.2%, 49.6%, and 17.5% respectively) with an average beta particle energy of 233 keV. These particles penetrate tissue only over a relatively short distance of 1-2 mm, allowing the delivery of high doses of radiation to the tumor while sparing surrounding normal tissue. ^{153}Sm has a half-life of 46 hours, but that portion of the drug not complexed to bone is completely eliminated through the kidneys within 6 hours of administration.

4.2 ANIMAL STUDIES

The efficacy of ^{153}Sm -EDTMP has been demonstrated in both murine and canine models of osteogenic sarcoma. Winderen et al. reported that ^{153}Sm -EDTMP could effectively treat orthotopic human osteosarcoma implanted in immunodeficient mice (5). Early studies with canine osteogenic sarcoma showed that ^{153}Sm -EDTMP caused a period of reversible pancytopenia. Subsequently, forty dogs with spontaneous osteogenic sarcomas were treated with one or two doses of 1 mCi/kg ^{153}Sm -EDTMP. Small lesions, metastatic lesions, and lesions of the axial skeleton responded well, while large lesions with minimal tumor bone formation responded poorly (6). The major toxicity was hematopoietic. In another study of canine osteosarcoma, there was a complete remission in 1 of 9 dogs treated with 1 mCi/kg (7). A dosimetry study in this animal model system showed that approximately 20 Gy were delivered to bone tumors by administration of 1-1.5 mCi/kg ^{153}Sm -EDTMP (8).

Our group has recently completed a two-phase study of eleven heavily pre-treated patients with osteosarcoma, who received tandem dosing of ¹⁵³Sm-EDTMP (15-16). With regards to patient outcome, though the study was terminated early based on protocol definition of clinical response, six patients showed radiographic stabilization. Toxicity was limited to hematologic suppression, manageable with stem cell transfusion support. We demonstrated that the total dose delivered to the tumor site with the initial “tracer” administered activity, and the subsequent higher, “treatment” administered activity displayed a strictly proportionate, linear relationship within each patient. Using this relationship, we plan to calculate the “treatment” administered activity necessary to achieve a planned total dose to tumor based on dosimetry mapping of the initial “tracer” activity. This allows a more accurate calculation and prediction of tumor exposure from a given infusion of ¹⁵³Sm-EDTMP.

These studies suggest that a significant quantity of ¹⁵³Sm-EDTMP can be given with manageable toxicity, and that treatment infusion needed to reach a planned total dose delivered to the tumor site can be predicted based on an individual patient’s dosimetry results after the initial tracer dose. Depending on the individual patient’s total dose exposure, we could then combine ¹⁵³Sm-EDTMP treatment with supplemental external beam radiation therapy. A recent paper reported that reasonable response times >3-5 years resulted with mean radiation dosing of 68.4 Gy (17). With tumoricidal dosing estimated to be 70-75 Gy, a proportion of this could be

given infusionally as ^{153}Sm -EDTMP, potentially decreasing the intensity of external beam radiation therapy needed to reach these target doses and minimizing local tissue damage.

The primary goal of this study will be to examine tumor response after radiation treatment via a combination of ^{153}Sm -EDTMP and external beam radiotherapy. A well-described characteristic of calcified osteogenic sarcoma lesions, as well as many bony metastases, is that despite necrosis or lack of viable tumor being detectable on histologic analysis, the tumor frequently does not shrink by radiographic imaging. Therefore the major clinical endpoint in evaluating clinical response will be lack of progression (stable disease or better by RECIST criteria). The favorable, manageable toxicity profile of ^{153}Sm -EDTMP would meet the needs of our study population of poor-risk, heavily pre-treated patients who might not otherwise be candidates for additional toxic therapy. This novel strategy of combined infusional and external-beam radiotherapy might prove to be an effective means for local control and offer significant clinical benefit.

4.4 HYPOXIA AND [^{18}F] FLUOROMISONIDAZOLE (^{18}F -MISO) PET

Hypoxia has been demonstrated in solid tumors and has been shown to be associated with resistance to chemotherapy, as well as potentially contributing to a more aggressive and invasive phenotype. One of the key players thought to orchestrate these changes is hypoxia inducible factor 1-alpha (HIF1- α), which acts as a transcription factor inducing production of numerous proteins that alter microenvironment and promote growth, neoangiogenesis, and invasion. Yang et al investigated HIF1- α expression in osteogenic sarcoma, and noted that 80% of tumors expressed HIF1- α , with increased microvessel density, a marker for hypoxia and likely resultant angiogenesis within tumor tissue (18). [^{18}F]-MISO PET scanning has been described in the literature as a tool to measure hypoxic areas in tumors (19). [^{18}F]-MISO accumulates in viable tissues preferentially when $\text{pO}_2 < 10$ mmHg and is dependent on nitroreductase activity within the cell. It is not dependent on blood flow, and is not retained in necrotic tissue. Studies have demonstrated changing hypoxia status in irradiated non-small cell lung cancer using this modality, as well as several papers in soft tissue sarcoma and head and neck cancers (20-24).

In our previous work, we demonstrated that changes in SUVmax measured by traditional FDG-PET scanning did not correlate with response to therapy. This suggests that FDG-PET may underestimate treatment response, possibly due to post-therapy inflammatory changes. Our interest in using [^{18}F]-MISO PET is two-fold. Our main question is whether tumors with higher [^{18}F]-MISO PET indices prior to treatment (increased hypoxia) might display less response to our proposed radiation therapy, which might ultimately allow us to predict patients likely to benefit. We also will investigate whether an *improvement* in oxygenation status (decrease in [^{18}F]-MISO indices) following treatment might correlate with histologic response to therapy given the lack of uptake demonstrated in necrotic tissue. In an effort to improve sensitivity of the [^{18}F]-MISO assessment of hypoxia and ensure attention to tumor volumes, we will combine the imaging with traditional [^{18}F]-FDG PET.

5.0 ELIGIBILITY CRITERIA

5.1 INCLUSION CRITERIA

5.1.1 Subjects will be between 10 and 65 years of age, inclusive.

5.1.2 Patient must have unresectable primary tumor or metastases (including tumors with an intralesional resection.)

5.1.2.1 For Stratum 1, patients must have a confirmed histologic diagnosis of osteosarcoma.

5.2.1.2 For Stratum 2, any histologically confirmed solid tumor diagnosis is eligible.

5.1.3 Patients must have measurable disease that is avid for phosphonate compounds as demonstrated by a positive Tc-99m bone scan. Not all lesions must be positive on bone scan.

5.1.4 Adequate organ function:

5.1.4.1 Adequate renal function, defined as a measured creatinine clearance >70 ml/min/1.73 m² or normal radioisotope GFR.

5.1.4.2 Adequate hematologic function, defined as a platelet count $>50,000/\text{mm}^3$ and an absolute neutrophil count $> 500/\text{mm}^3$

5.1.5 Life expectancy of > 8 weeks

5.1.6 Karnofsky performance status $> 50\%$

5.1.7 Patients must have recovered from the effects of any prior chemotherapy, as determined by the treating physician and studyteam, based in part on organ function defined above.

5.1.8 A stem cell product collected prior to the infusion of ¹⁵³Sm-EDTMP must be available, either by peripheral stem cell mobilization or bone marrow harvest prior to trial entry. A minimum of 2×10^6 CD34⁺ cells/kg ideal body weight is required.

5.1.9 The patient and/or the patient's legally authorized guardian must acknowledge in writing that consent to become a study subject has been obtained, in accordance with institutional policies approved by the U.S. Department of Health and Human Services.

5.2 EXCLUSION CRITERIA

5.2.1 Patients must not be pregnant or breastfeeding. Sexually active patients are strongly advised to use accepted, effective forms of contraception.

5.2.2 Patients who have received prior radiotherapy to all areas of current active disease are ineligible.

5.3 INFORMED CONSENT

Informed consent will be obtained from the parents or legal guardian of minor children. Patients over the age of 18 years will provide their own informed consent. Either assent or

consent will also be obtained at a developmentally appropriate level from subjects that are minor children.

5.4 REGISTRATION

To register a patient, the following documents should be completed by the Research Nurse or Study Coordinator and faxed [contact]) or emailed ([contact]) to the Coordinating Center:

- Fax cover sheet
- Registration form
- Signed patient consent form
- HIPAA authorization form
- Eligibility screening checklist

Copy of required screening tests and scans The Coordinating Center will then verify eligibility and complete the registration process, by:

- Assigning a patient study number
- Registering the patient on the treatment portion of the study with the Sidney Kimmel Comprehensive Cancer Center's Clinical Research Office
- Faxing or e-mailing the patient study number to the participating site
- Calling or e-mailing the research nurse or data manager at the participating site, verbally confirming registration and the last eligible start date for treatment.

6.0 TREATMENT PLAN

6.1 PRETREATMENT EVALUATION

6.1.1 History and physical examination, including symptoms, height, weight, and body surface area

6.1.2 Laboratory evaluation, including CBC with differential and platelet count, comprehensive metabolic panel, urinalysis, 24-hour urine for creatinine clearance, phosphorus, magnesium, LDH, serum C-telopeptides (JHH Pathology test code 6315) and parathyroid hormone. Alkaline phosphatase and LDH will be fractionated if elevated to determine the contribution of bone isoforms (Quest referral tests).

6.1.3 Radiographic evaluation: chest X-ray, Tc-99m bone scan, and other imaging that may include CT, MRI, and/or PET/CT scans of primary tumor and any large metastases.

6.1.4 Cardiac evaluation: baseline EKG to be obtained prior to treatment.

6.1.5 As part of the study protocol, subjects will undergo a pre-treatment [¹⁸F]-MISO/[¹⁸F]-FDG whole body PET scanning as delineated in section 6.2.4.

6.2 OVERALL TREATMENT PLAN

This is a treatment protocol to establish the safety and efficacy of radiation therapy consisting of high-dose ^{153}Sm -EDTMP and external beam radiotherapy for the treatment of high-risk osteogenic sarcoma and solid tumors with bony metastases. The primary endpoint will be clinical response of tumor lesions, defined as either stable disease or decrease in the size of the tumor by radiographic imaging (which may include CT or MRI) using RECIST 1.1 criteria. Progression will be defined as appearance of new lesions or expansion of current lesions by 20% as per RECIST 1.1 criteria. In some patients, additional information on clinical response may be obtained from histology (percent tumor necrosis) in cases where patients proceed to resection or biopsy following radiation therapy. Other treatment endpoints include progression-free and overall survival. We will obtain post-treatment [^{18}F]-MISO and [^{18}F] FDG PET scans to be analyzed but these images will not be used to define clinical response.

The first administered activity of ^{153}Sm -EDTMP will be a low “tracer” infusion administered at 1 mCi/kg on Day 1. Using the 3-dimensional dosimetry package 3D-RD, we will perform three-dimensional dosimetry using SPECT images after administration of the “tracer” activity to determine the distribution of dose delivered to the tumor and the surrounding normal tissues. As quickly as feasible (goal is within seven days), using the dosimetric results from the tracer administration, a combined treatment plan will be designed aimed at delivering the target dose to the entire tumor. This plan will be designed using methodology uniquely available at Hopkins (3D-RD software); we will import the 3-dimensional absorbed dose map resulting from ^{153}Sm -EDTMP therapy, adjusted to correspond to the fractionation schedule used in external beam radiotherapy, into the external beam planning system (Pinnacle), by fusing (registering) the SPECT/CT and absorbed dose map with the external beam planning CT, allowing a treatment plan to be generated from the combination of (1) scaling of the tracer absorbed dose map to the requisite ^{153}Sm therapeutic activity and (2) external beam fields designed to optimally complement the radiopharmaceutical absorbed dose map to deliver a target of 75 Gy to each and every tumor voxel while respecting normal organ constraints (25).

The first portion of the combined plan, that is, the second, “treatment” ^{153}Sm -EDTMP infusion, will then be implemented on Day 8. Maximum activity administered will be 30 mCi/kg, which is the maximally tolerated dose permitting recovery of myelosuppression with auto-stem cell infusion (14). After the “treatment” infusion, SPECT scans will again be performed to confirm total dose delivered and subsequently adjust the external beam portion of the treatment plan, as necessary. External beam radiotherapy will begin as early as possible between Days 15 and 22. The total dose to be used will be modified based on surrounding tissue tolerances. On Day 24, previously harvested autologous peripheral blood or bone marrow stem cells will be infused in order to ameliorate the expected myelosuppression. External beam radiation therapy will not be administered on Day 24 (anticipated to be a Friday), nor on Days 25 or 26, in order to provide time for infused hematopoietic stem cells to home to the bone marrow and leave the circulation.

Patients will be reimaged one month following completion of external beam radiation by CT/MRI for evidence of clinical response (defined as stable disease or better by RECIST 1.1 criteria) or disease progression. In the event of progression of a single lesion, local therapy such as radiofrequency ablation or cryoablation may be provided so that the response of stabilized lesions can continue to be monitored. If suspicious lesions remain on

thoracic CT scan or on MRI of the primary site after the completion of therapy, further evaluation by biopsy may be clinically indicated, and potentially surgical intervention pursued if persistent disease is found. Percent necrosis of any resected tumor will be evaluated pathologically.

6.2.1 Stem cell collection

Although ifosfamide mobilization is preferred, any method for obtaining autologous hematopoietic stem cells (HSC) is acceptable. The timing of stem cell collection is at the discretion of the treating physician, as long as stem cells are collected prior to administration of $^{153}\text{Sm-EDTMP}$.

Recommended, but not required, approach if prior collection not available and no evidence of Ifosfamide resistance: Peripheral blood stem cells will be collected as per standard protocols after a cycle of Ifosfamide given as a single agent, at a dose of $3 \text{ g/m}^2/\text{day}$ for 5 days with MESNA. The MESNA will be administered according to institutional standards.

G-CSF will be administered daily upon completion of the chemotherapy at a dose of $10 \mu\text{g/kg/day}$ subcutaneously. Peripheral blood CD34^+ cell count will be monitored daily beginning on Day 7 after chemotherapy is completed, or when ANC begins to rise, and pheresis will be performed when indicated.

Collection of $5 \times 10^6 \text{ CD34}^+$ cells/kg will be the goal, with the product split into 2 aliquots and stored frozen until needed. If more than $6 \times 10^6 \text{ CD34}^+$ cells/kg are collected, three aliquots will be stored. Pheresis on consecutive days will be performed if necessary to meet this target. A minimum collection of $2 \times 10^6 \text{ CD34}^+$ cells/kg will be required for treatment with $^{153}\text{Sm-EDTMP}$.

If peripheral stem cell collection is not feasible or cell mobilization is inadequate, bone marrow harvest in the operating room under general anesthesia will be an alternative source and may be performed as per standard protocols.

6.2.2 Radiation Dosimetry

^{153}Sm SPECT/CT imaging with the CT acquisition in high resolution mode will be collected at approximately 4 hours after infusion of the “tracer” dose; SPECT/CT imaging with CT acquisition in attenuation correction (low-res.) mode will be performed at 24 and 48 hours post-infusion to determine the absorbed dose for a given administered activity of $^{153}\text{Sm-EDTMP}$. The 24 and 48 hour post-infusion SPECT/CT scans can be obtained any time one and two days after treatment, as long as the specific number of hours post-infusion is recorded. We will use the in-house developed software package, 3D-RD, to calculate lesion absorbed dose maps that will be transferred to the external radiotherapy software so that a combined radiotherapy treatment plan is generated. The combined treatment plan will be used to determine the administered activity and external beam radiation needed to deliver a total combined, absorbed dose 75 Gy to the lesion while respecting toxicity constraints to adjacent dose-limiting tissues. This approach is based on

previous studies showing that lesion absorbed scales with administered activity (16). We have also demonstrated the ability to adjust for dose rates by using the biologic effective dose (BED) formalism and thereby incorporate radiopharmaceutical therapy into an external radiotherapy treatment plan (25-26). ^{153}Sm planar imaging of the abdomen will be performed at 1 and 2 hours after the “treatment” infusion to allow an assessment of radiation delivered to kidneys. SPECT/CT imaging will also be collected at three later time-points after the “treatment” administration: approximately 4 hours, 24 hours, and 48 hours. The 24 and 48 hour post-infusion scans can again be obtained at any time on the first and second day after treatment, as long as the specific number of hours post-infusion is recorded. If lesion dosimetry from the therapy study is inconsistent with the low dose projection, the combined treatment plan will be revised accordingly. This treatment dose will not exceed 30 mCi/kg, the dose previously delineated by Anderson, et al as the maximally tolerated dose for reversible hematologic toxicity (14).

Based on experience and patient tolerability, the number and frequency of SPECT/CT scans may be modified over the course of the trial.

6.2.3 Autologous Peripheral Blood Stem Cell or Bone Marrow Infusion

Sixteen days after administration of the treatment dose of ^{153}Sm -EDTMP, autologous peripheral blood stem cells or bone marrow will be reinfused according to standard institutional protocols.

6.2.4. Acquisition of [^{18}F]-MISO/ [^{18}F]-FDG PET *imaging*

We plan to obtain investigational imaging of tumor hypoxia using [^{18}F]-MISO in combination with traditional [^{18}F]-FDG PET imaging. Following treatment, we will analyze the [^{18}F]-MISO PET data to determine any correlation to clinical response defined by traditional RECIST criteria with CT/MRI imaging, and percent necrosis as determined by histology as detailed in section 10.1.

Protocol: Patients will undergo FDG-PET/CT according to standard protocols, and [^{18}F]-MISO PET scanning as per the described protocol (21). Images will be compared side-by-side to ensure accurate inclusion of tumor fields, as described by Rajendran (23). Four venous blood samples will be collected five minutes apart to normalize Tumor/Blood ratios as described in reference 23. Additionally, ratios between tumor and contralateral soft tissue, as well as tumor/adjacent muscle will be obtained. Ratios of greater than 1.2 will be considered hypoxic. Ratios will be converted to milliliter volume to measure hypoxic tumor volume. We will discount any lesions occurring in the liver or bladder from study due to inaccurate readings previously reported.

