11.0 STATISTICAL CONSIDERATIONS

11.1 OVERVIEW

This protocol will assess the proportion of clinical tumor responses, defined as progression-free survival at 6 months, and the toxicities associated with high-dose ^{153}Sm -EDTMP (MTD at 30 mCi/kg) after an initial lower dose of the agent along with external beam radiation therapy in patients with high-risk osteogenic sarcoma.

Primary objective: The primary objective of this study is to determine if the addition of external beam radiation therapy to infusional ^{153}Sm -EDTMP can delay the progression of target lesions. The primary endpoint is 6-month progression free survival (PFS). It is a combined effect of the entire treatment. To be evaluable, patients must meet all eligibility criteria, including signing a consent form, and have completed treatment according to protocol without major deviations. Patients who are enrolled but unevaluable will be replaced on the study. Only patients enrolled on Stratum 1 (i.e., with a diagnosis of osteosarcoma) will be evaluated for the Primary Objective.

Secondary objectives:

1. Describe the short and long-term toxicity profile of combined treatment with ^{153}Sm -EDTMP and external beam radiation therapy.
2. Estimate the local control rate. (Stratum 1 only)
3. Determine the overall survival (OS). (Stratum 1 only)
4. Describe the distribution of absorbed doses delivered to each targeted lesion and the distribution of equivalent uniform doses delivered to each patient.
5. Model the relationship between absorbed doses and time to progression.
6. Determine the correlation of hypoxic volume and maximum tumor/blood ratio obtained by [^{18}F]-MISO PET scanning with patient outcomes.

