Toxicities will be graded according to CTCAE v4.0 and the RTOG Cooperative Group Common Toxicity Criteria, and attributable toxicities grade 3 or higher will be recorded. For purposes of evaluation, we will consider toxicities resulting from the administration of ¹⁵³Sm-EDTMP separately from toxicities resulting after initiation of external beam radiation therapy. [However, we will hold accrual after enrollment of five patients to evaluate cumulative toxicity from the combined regimen.] Adjustments to external beam therapy in response to toxicity would be made in accordance with standard Radiation Oncology treatment protocols and clinical judgment.

11.3.3 Describe the distribution of absorbed doses delivered to each targeted lesion and the distribution of equivalent uniform doses delivered to each patient.

The total absorbed dose delivered to each targeted lesion will be limited by the tolerance of surrounding normal tissue. We will produce histograms showing the distribution of radiation absorbed doses by lesion, and summarize the results by patient for the lesion receiving the lowest absorbed dose in each patient. With a sample size of 20 patients, we will be able to estimate the proportion of patients whose lesions are all treated to an absorbed dose of ≥ 80 Gy with a precision of $\pm 23\%$.

11.3.4 Model the relationship between absorbed dose and time to progression for patients enrolled in Stratum 1.

We expect a total dose of 80 to 100 Gy to produce a local control rate of 80%, while a total absorbed dose of 60 to 70 Gy may produce a local control rate of 50 – 70%, and the local control rate would decline steeply at lower absorbed doses. We will use a generalized mixed effects model treating dose and time as fixed effects and the random effect of individual patients for the outcome of progression of each targeted lesion. If at least 10 patients have at least one lesion that receives a radiation dose with similar effectiveness to our historical control experience, and at least one lesion receiving the targeted dose, this analysis would have 80% power to demonstrate a significant dose-response with alpha 0.05.

11.3.5 Determine overall and progression-free survival for patients enrolled in Stratum 1.

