Survival curves will be estimated by using the Kaplan-Meier method. Progression-free survival is defined as time from registration to the first observation (documentation) of disease progression or death. Patients who are lost to follow-up will be censored for determination of PFS on the date of their last evaluations. Overall survival is defined as time from registration to death due to any cause.

11.3.6 Determine correlation of hypoxic volume and maximum tumor/blood ratio obtained by [¹⁸F]-MISO PET scanning with patient outcomes.

Cox regression analysis will be performed to measure association between hypoxia based on HV and max T/B ratio with Kaplan-Meier survival and time-to-progression curves. Additional regression analysis will be performed to evaluate the link between hypoxic indices and uptake of ¹⁵³Sm-EDTMP and clinical response based on radiologic response and presence of necrosis on histology.

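### The hypoxia regressions in 11.3.6 name no study population and no stratum term, so a combined fit could reflect tumour type rather than hypoxia; osteosarcoma-only should be the main analysis

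*Combined protocol and SAP*

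**What the plan says.** Both strata are scanned. Section 6.1.5 begins "As part of the study protocol, subjects will undergo a pre-treatment" and goes on to the combined F-MISO/FDG scan. Neither that section nor 6.2.4, 6.3.4 or the schedule tables distinguishes the strata. The eligibility text reads "For Stratum 2, any histologically confirmed solid tumor diagnosis is eligible".

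The hypoxia analysis appears in four places, none with a stratum label:

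- 3.2.2: image before and after treatment and "compare with clinical response as measured by radiographic imaging and/or histology".
- 6.2.4: "Following treatment, we will analyze the [^{18}F]-MISO PET data to determine any correlation to clinical response defined by traditional RECIST criteria", and with percent necrosis.
- 11.1, secondary objective 6: "Determine the correlation of hypoxic volume and maximum tumor/blood ratio obtained by" F-MISO PET with patient outcomes.
- 11.3.6: Cox regression relating hypoxic volume and maximum tumour/blood ratio to survival and time to progression, and then "Additional regression analysis will be performed to evaluate the link between hypoxic indices and uptake of" samarium, and clinical response judged by radiology and necrosis.

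Other items do carry a limit. Section 3.2.5, headed as Stratum 1 only, reads "To observe overall survival and time to progression in patients treated with combined infusional" samarium and external beam treatment. Section 11.3.4 is headed "Model the relationship between absorbed dose and time to progression for patients enrolled in Stratum 1", and the heading of 11.3.5 limits overall and progression-free survival to Stratum 1.

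**The concern.** Stratum is a potential confounder that the trial already records, and 11.3.6 does not use it. The protocol's own background explains why it could matter. The agent goes to sites of new bone formation (4.1), and in dogs the large lesions with little tumour bone responded poorly (4.2). Uptake and response may therefore depend on how much bone a tumour forms, which can differ between osteosarcoma and an arbitrary solid tumour. If hypoxia also differs by tumour type, a coefficient fitted to everyone mixes the hypoxia effect within a tumour type with differences between types. It can then show an association where there is none, or hide a real one.

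Section 4.4 makes the relation between pre-treatment hypoxia and response its main F-MISO question, with the longer-term hope of identifying patients likely to benefit. An index that only separates osteosarcoma from other tumours would not serve that purpose.

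**Working it through.** **Plan figures.** The plan gives no sample size, power or precision for the hypoxia analyses, so there is no figure of its own to reproduce. Two of its numbers feed the illustration.

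- Stratum 1 hazard at the 35% benchmark (11.3.1): −ln(0.35)/6 = 0.175 per month. The same formula gives −ln(0.158)/6 = 0.308 for the reference, as the plan states.
- Numbers: 11.3.1 accrues 4 × 5 = 20 in Stratum 1, and 11.4 expects 5 × 5 = 25 in the study. If 11.4 covers both strata, Stratum 2 has 25 − 20 = 5. No Stratum 2 size is stated, so 20 + 10 was also run.

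**Assumptions, not in the documents.** The hypoxia index is normal with no effect on progression. Its mean differs by 0 to 1.5 SD between strata. The Stratum 2 hazard is equal to, one half or one third of that in Stratum 1. Survival is exponential, with censoring uniform over 12 to 72 months. The yardstick is a Cox score test at two-sided 5%; 11.3.6 states no alpha.

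**Cox test, false-positive rate, 4,000 replicates per scenario, 20 + 5 patients.**

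| Hypoxia difference | Hazard ratio | Pooled | Stratified | Stratum 1 only |
|---|---|---|---|---|
| 0 | 0.33 | 5.6% | 6.5% | 6.1% |
| 0.5 SD | 0.5 | 6.5% | 5.9% | 6.4% |
| 0.5 SD | 0.33 | 7.1% | 6.1% | 6.2% |
| 1 SD | 1 | 5.6% | 5.5% | 5.7% |
| 1 SD | 0.5 | 8.4% | 5.1% | 5.4% |
| 1 SD | 0.33 | 12.3% | 5.6% | 5.9% |
| 1.5 SD | 0.5 | 10.5% | 5.1% | 5.3% |
| 1.5 SD | 0.33 | 18.8% | 5.2% | 5.4% |

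The excess should be read against roughly 5–6%, which is what this test gives at this size with no confounding. Where the strata differ in hazard only or in hypoxia only, the pooled test stays near that level. If Stratum 2 has the higher hazard instead, the inflation is somewhat smaller. With 20 + 10 patients the pooled rates are 7–9%, 13–20% and 15–33% for the three shifts.

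**Uptake regression** (linear model, no true effect, 20,000 replicates, index and uptake shifted in opposite directions):

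| Shift in each | Pooled, 20 + 5 | Pooled, 20 + 10 | With stratum term |
|---|---|---|---|
| 0.5 SD | 5–6% | 5–6% | 5% |
| 1 SD | 10% | 16% | 5% |
| 1.5 SD | 26% | 47% | 5% |

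**Does a stratum term suffice?** The runs above make Stratum 2 homogeneous, although it is open to any solid tumour. Suppose instead that it holds two tumour types: one with a higher hazard and higher index, the other with a lower hazard and lower index. With 2-fold and 1 SD contrasts, the stratified Cox test rejects about 7% (20 + 5) and 12–13% (20 + 10). With 3-fold and 1.5 SD contrasts it rejects 10% and 28%. Stratum 1 alone stays near 6%.

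**The case against.** The strongest reply is that pooling is nowhere written. It is inferred from a missing label in a document that does not label consistently: secondary objective 5 in 11.1, the absorbed-dose model, also has no label there, yet 11.3.4 limits it to Stratum 1. The survival part of 11.3.6 refers to survival curves, and the only such curves planned are those of 11.3.5, immediately above and limited to Stratum 1. Section 11.2 gives Stratum 2 a role in toxicity, feasibility and, if possible, response rates, and does not mention hypoxia. Every Stratum 2 input in the illustration is assumed, and the work is exploratory.

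Most of this stands. A reader might infer that the plan prescribes a pooled survival model; the documents do not support that, because the Cox models may inherit the limit of 11.3.5. The reply does not settle the response, necrosis and uptake regressions, for which no Stratum 1 limit appears anywhere. If Stratum 1 was intended throughout, 11.3.6 still has to say so.

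A reader might also infer that stratifying by the trial's two strata would cure the problem. It removes only the contrast between osteosarcoma and everything else, not differences among histologies within Stratum 2.

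**Conclusion.** The point holds as a gap in 11.3.6: no analysis population and no stratum term for the hypoxia models, clearest for response, necrosis and uptake and ambiguous for survival.

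The size is unknown, because the documents give no hypoxia level, hazard or number of patients for Stratum 2. Under the assumptions above with 20 + 5 patients and a 2- to 3-fold hazard difference, a pooled 5% Cox test would reject about 6–7%, 7–12% or 10–19% of the time for hypoxia differences of 0.5, 1 and 1.5 SD. There is essentially no inflation unless the strata differ in both hypoxia and outcome. The larger rates come from 10 Stratum 2 patients or from the largest shifts, and should not be taken as the expected effect.

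It would also be wrong to infer any consequence for the main result. The primary endpoint is assessed in Stratum 1 only, and neither it nor the stopping rules use these models. This is a worthwhile repair to an exploratory secondary analysis.

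**What to change.** In 11.3.6, state that the Stratum 1 (osteosarcoma) estimate is the main analysis for every hypoxia model: survival, time to progression, response, necrosis and samarium uptake. Label any analysis that combines the strata as supportive. In it, stratify the Cox models by stratum and add a stratum covariate to the other regressions where it can be estimated; it may not be for necrosis, which is available only for patients who go on to resection or biopsy. Note that this adjustment does not remove differences between histologies within Stratum 2. Refer to the same statement from 3.2.2, 6.2.4 and item 6 of 11.1.

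This takes a few sentences and needs no new data, since stratum is fixed by diagnosis at entry. The price is a smaller main hypoxia analysis: 20 patients rather than perhaps 25, if 11.4 counts both strata, and so somewhat less precision.
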